Exclusion criteria include prior stroke with persisting motor impairment or disability; limited resources or illness that will not enable a return to living outside of a facility; any medical condition that had limited daily physical activity to walking no more than 2 blocks outdoors prior to the stroke (e.g., claudication, congestive heart failure or lower extremity pain); history of dementia or MMSE score <24; history of hepatitis or elevated hepatic transaminases or bilirubin; history of renal insufficiency or serum creatinine over 1.6; and cancer or other chronic illness that makes 3-year survival unlikely or will detract from the ability to carry out exercise and skills practice.

Randomization:

Participants will be assigned to the control or experimental group using a 1:1 computer-generated randomized allocation schedule in the REDCap clinical database. Assignment (for both research sites) occurs automatically upon the entry of eligibility criteria.

All members of the research team and the subjects will be blinded as to allocation. The study statistician and the rest of the Safety Committee will have access to the assignment if necessary (e.g., adverse drug reaction).

Each site will enter 20-25 subjects, approximately half into each of the trial arms. Entries will be accomplished within 30 months with follow-up assessments and data analyses by the end of 36 months.

Baseline Studies:

We will collect age, gender, body mass index, ethnicity, living place, work status, caregiver support, date of stroke, date of transfer for inpatient rehabilitation, lesion type (TOAST) and location, personal risk factors for stroke, medications, and FIM for level of pre-stroke walking and ADLs. We will measure the National Institutes of Health Stroke Scale (NIHSS), British Medical Council manual muscle exam for eligibility, motor FIM score, 10-m

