walking speed, 6-min walking distance, a video-recorded assessment of upper extremity kinematics that does not show the subject's face, and Action Research Arm Test (ARAT). We will record the average two blood pressures and heart rates on the day of entry and the most recent HbgA1c and lipid panel, liver function tests, creatinine/BUN, and MRI/CT imaging results from the inpatient rehabilitation medical record. If liver function tests or creatinine cannot be found, the tests will be obtained at the outpatient research site as a cost to the study. [name] will review each imaging study to localize the relevant stroke lesion by consensus. An email address and phone number for the patient and a close contact will be kept separate from the clinical database by the coordinator.

Interventions:

Maraviroc: Medications are often in flux during inpatient rehabilitation, so Maraviroc or placebo will be started within two weeks of discharge, which most often will occur from 4-6 weeks after stroke onset. A 1-month supply of capsules will be handed to participants after the Consent has been signed, baseline measurements obtained, and randomization assigned, usually on the same day. The second 1-mo supply will be provided during a scheduled interim measurement assessment at UCLA near the end of the 4th week on medication. Pill counts will be taken on the returned bottle. Participants will take either *Maraviroc or a placebo at a dose of 300 mg at 6-8AM*. The capsules will be supplied by the UCLA, Burke and Yale pharmacies to each respective site and used under an IND and IRB protocol as required by each institution.

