Based upon Pfizer's reports on premarketing and post marketing studies of Maraviroc and our review of the literature, no dose adjustment is necessary in patients with even mild-to-moderate renal impairment. The drug does not affect the QT interval. At high doses (600mg or more), it may induce orthostatic hypotension, so it is recommended that *users who also take an anti-hypertensive medication be asked about symptoms of orthostatic hypotension*. Of note, 8% of patients in active and placebo drug groups described orthostatic symptoms in a large trial. In HIV trials, 1.3% of subjects had cardiovascular events, more than in the placebo group, but the link to the drug was unclear and symptoms occurred only in those with known cardiac disease. Also, no greater incidence of infection, rash or other CNS symptoms was noted in these subjects. An occasional Stevens-Johnson syndrome and drug rash with eosinophilia and systemic symptoms did occur (seen only in post marketing surveillance, not in controlled trials), so *complaints of rash, fever, joint or muscle aches, blisters, facial edema, etc. will be part of our weekly phone call surveillance plan*. Participants will be told to stop their medication immediately should such symptoms occur and their physician notified. Of note, St John's wort should not be used with the medication since it decreases the concentration of Maraviroc

The drug is metabolized by the liver, so using it in persons with more than mild hepatic disease, especially in the presence of a CYP3A inhibitor, would have to be closely monitored; our participants will be free of hepatic, as well as renal impairment. The recommendation from the FDA is to obtain liver function tests prior to starting the drug and again should symptoms such as rash or hepatitis occur. This rather rare adverse reaction tends to occur at about one month after starting the medication (in less than 4% on the drug or placebo) , so *we will obtain a bilirubin and transaminases at the planned 1-month follow up.*

Adverse events related to the medication assignment, to rehabilitation practice or to other causes will be adjudicated by the Safety Committee with input from the PI.

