Rehabilitation therapy: All participants will have routine outpatient or home health physical and occupational therapy after inpatient discharge as prescribed by their physicians. Each group will be contacted weekly by phone by UCLA staff only to help maintain interest in the trial, count the number of usual care physical and occupational therapy completed, assure use of the assigned medication, ask about possible adverse reactions, and to encourage them to be active. The UCLA coordinator will obtain this information and provide the feedback using a

standard script and checklist.

A unique aspect of this trial is a telerehabilitation component that aims to give feedback to all participants to practice with the affected arm and walk daily. All participants will be asked to wear an ankle sensor (Fitbit) that downloads to a computer we supply to each subject. We record lower extremity activity, including walking and cycling. Data includes daily sedentary and active time, walking speed and distance. The walking data is sent to a HIPAA compliant cloud server provided by a commercial company, FitaBase. The coordinator at each site will show each study subject and caregiver how to put on and charge the sensors. At the weekly call, participants will be reminded to try to build up to walking at least 3 times a day for at least 10 minutes per bout and reduce sedentary time. Behavioral modification techniques that we have been using successfully, based on sensor data, will be employed. All such feedback will be provided by the UCLA study group.

Participants will also be given a LEAP Motion Controller device that sits in the bottom of a 12x18" box covered by a plastic lid. This simple system enables us to monitor practice of reaching and grasping with the affected upper extremity in the home. At the weekly call from a UCLA study staff person, they will be encouraged to perform 20 minutes daily of reach, grasp and pinch actions with small common items and practice bringing the affected hand to the mouth. Items will be moved from one corner of the rectangular top to another in a fixed sequence. A unique feature of this trial is that we will have ground truth about how much they did practice, which may enable a dose-response and responder-nonresponder analysis. For example, if a subject is taking the active medication, but never practices, outcomes may be less positive than for the person who does practice as prescribed.

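### The targeted orthostatic-symptom question goes to antihypertensive users only and has no schedule, and medications are listed only at entry, so detection in everyone else rests on the general weekly adverse-event query

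*Combined protocol and SAP*

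**What the plan says.** The Maraviroc part of Interventions covers three safety matters and attaches an action to each.

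- **Orthostatic hypotension.** The plan says "At high doses (600mg or more), it may induce orthostatic hypotension" and recommends that "users who also take an anti-hypertensive medication be asked about symptoms of orthostatic hypotension". It adds that "8% of patients in active and placebo drug groups described orthostatic symptoms in a large trial". The study dose is "Maraviroc or a placebo at a dose of 300 mg at 6-8AM".
- **Rash and hypersensitivity.** Here the action has a place and a frequency: "complaints of rash, fever, joint or muscle aches, blisters, facial edema, etc. will be part of our weekly phone call surveillance plan".
- **Liver.** Bilirubin and transaminases are repeated at the one-month follow-up.

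Baseline Studies lists "personal risk factors for stroke, medications, and FIM for level of pre-stroke walking and ADLs" and states "We will record the average two blood pressures and heart rates on the day of entry". Neither medications nor blood pressure appears again in the text or in the Table of measurements. The Table does repeat the change in heart rate with the six-minute walk during treatment.

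Under Rehabilitation therapy, both groups are telephoned weekly from a script and checklist. The tasks of the call include to "assure use of the assigned medication, ask about possible adverse reactions, and to encourage them to be active". Later in the same section, a scripted weekly query about medical complications is described, with immediate reporting to the lead investigator and an interview by the responsible site investigator. The Table places adverse-event assessment at the weekly follow-up for two months, which spans the eight weeks on drug.

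**The concern.** Of the three safety actions, the orthostatic one alone depends on co-medication and alone lacks a schedule. The only stated source for antihypertensive use is the entry medication list. The listed tasks of the weekly call do not include changes in medication, so a participant who starts an antihypertensive on treatment has no stated route to the targeted question. The same gap affects the plan's own safeguard on interactions. Background keeps out patients who take CYP3A4 inducers or inhibitors at entry, and Interventions warns against St John's wort, but no step is described that would detect such an agent begun later.

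A prompted question usually yields more reports than a general one. If one subgroup is prompted and the rest are not, the reported frequency depends partly on who was prompted. This matters more here than in many trials, because participants are hemiparetic, may enter with an ambulation FIM score of 3, and are encouraged each week to walk at least three times a day. Light-headedness on standing bears on falls, and falls are not among the symptoms named for the call.

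**Working it through.** The plan gives no sample size, power or error rate for this outcome, so there is no stated figure to reproduce. The check is a comparison of sections, followed by arithmetic for scale.

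**Where each item is collected**

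| Item | At entry | During the 8 weeks on drug |
|---|---|---|
| Targeted orthostatic question | not stated | antihypertensive users; no schedule |
| Medications | yes | none stated |
| Blood pressure | yes | none stated |
| General adverse-event query | – | weekly, all participants |
| Rash and hypersensitivity symptoms | – | weekly, named for the call |
| Orthostatic symptoms or falls named for the weekly call | – | no (the list is open-ended) |

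**Expected number with symptoms**

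Inputs: p = 0.08 (Interventions); n = 30 evaluable per arm, or 33 if the 66 planned enrolments are split equally (Statistical Analyses).

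- Expected cases per arm, n × p: 30 × 0.08 = 2.4; 33 × 0.08 = 2.64.
- Chance of at least one case in an arm, 1 − (1 − p)^n: 1 − 0.92^30 = 0.92; 1 − 0.92^33 = 0.94.

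**Share reached by the targeted question**

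The share f taking antihypertensives is not in the documents. I assume 30% to 90%, and the same 8% in users and non-users. With n = 30:

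| f | Asked per arm (30 × f) | Cases among those asked (× 0.08) | Cases left to the general query (2.4 minus that) | Chance of at least one case among those asked |
|---|---|---|---|---|
| 30% | 9 | 0.72 | 1.68 | 0.53 |
| 50% | 15 | 1.20 | 1.20 | 0.71 |
| 70% | 21 | 1.68 | 0.72 | 0.83 |
| 90% | 27 | 2.16 | 0.24 | 0.89 |

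Cases left to the general query are not necessarily missed; they depend on a less specific question.

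**What uniform questioning could show**

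Power for two proportions with 30 per arm, two-sided 5%, is Φ[(Δ − 1.96 × s0) / s1], where s0 = √(2 × p̄ × (1 − p̄)/30) and s1 = √((p1(1 − p1) + p2(1 − p2))/30).

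- 8% v 16%: Δ = 0.08, s0 = 0.0839, s1 = 0.0833; power about 16%.
- 8% v 24%: Δ = 0.16, s0 = 0.0947, s1 = 0.0924; power about 39%.

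Even with everyone asked, the gain is in description and not in formal comparison.

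**Would the existing visits supply an on-drug reading?**

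Outcome Measurements allows the 8-week assessment up to five days after the final dose, and Background gives a terminal half-life of 14 to 18 hours. Five days is 120 hours: 120/18 = 6.7 and 120/14 = 8.6 half-lives. A late 8-week visit could be effectively off drug; only the 4-week visit is reliably on drug.

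**The case against.** The strongest reply is that every participant is followed. Both groups receive a scripted weekly query about adverse reactions and medical complications, reports go at once to an investigator, and the Safety Committee adjudicates. This stands. A reader might infer that orthostatic hypotension is not followed during treatment, or that non-users are left to spontaneous report. The documents support neither, because the weekly query is solicited and covers everyone.

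The script itself is not in the documents, and the list of named symptoms is open-ended. The plan also relays a recommendation to ask antihypertensive users without saying that others will not be asked. So it cannot be said that non-users, or later starters, would never get the question. What can be said is that the plan names one group to ask and describes no way of updating who belongs to it.

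The clinical weight is reduced by the plan's own figures: the risk is placed at 600 mg or more, and the cited trial had 8% in both groups, which shows no excess on drug. This also stands, although the plan still thought the question worth asking.

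A reader might infer bias between arms. Allocation is randomised and blinded and the same rule applies to both arms, so none is demonstrated. A reader might also take the remark about medications being in flux as evidence that entry medication lists go out of date on study. That remark describes the inpatient stay and is the reason given for starting study drug after discharge.

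Finally, a single blood pressure reading without a postural component would not measure orthostatic change, and a late 8-week reading may be off drug. That is a fair reason not to rest the fix on blood pressure.

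**Conclusion.** The point holds in a limited form. The targeted question is tied to antihypertensive use, has no schedule, and rests on a medication list described only at entry. For other participants, and for those who start an antihypertensive or interacting drug on treatment, detection depends on a general weekly query whose named symptoms omit orthostatic symptoms and falls. The consequence is uneven, probably incomplete ascertainment common to both arms.

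The size is small in absolute terms. Of 2.4 expected cases per arm of 30, between about 0.2 and 1.7 would depend on the general query. This range rests on the assumed 30% to 90% antihypertensive use and on an equal 8% rate in users and non-users; the 8% itself comes from another trial. The change is worth making because it is cheap and the participants are at risk of falling, not because a drug effect has been missed or could be tested in this sample.

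**What to change.** 1. Put one question on orthostatic symptoms and falls in the existing weekly script, in the same words for every participant in both arms.
2. Add one weekly item on medicines started, stopped or changed since the last call, so that antihypertensives and interacting drugs begun on treatment are recorded.
3. Send positive answers through the reporting route already described for the weekly call.
4. Reconcile Baseline Studies, Interventions (Maraviroc and Rehabilitation therapy), Outcome Measurements and the Table on who is asked, when, and how the answer is recorded.

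The cost is about a minute more per call and no extra staff. More minor symptoms will be recorded in both arms, so the resulting frequencies should be reported descriptively by arm.

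Whether to record blood pressure on treatment, and any clinical action on the findings, is for the sponsor and the Safety Committee. If they choose to record it, they should allow for the timing of the 8-week visit shown above.

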A data manager at UCLA will review all incoming data from the 3 sites for completeness and quality, as well as ensure proper use of the systems (e.g. make sure devices are charged regularly, automatic data uploads occur without problems, and practice data are processed correctly). The study staff at each site will assist the UCLA staff to help solve technical problems with the equipment and interact with subjects around difficulties in patient participation. At the weekly call by UCLA staff, participants will be queried from a script about any possible medical complications. Such potential adverse events will be immediately reported to [name] who will contact his participants or contact the local PI at Burke or Yale to interview their subjects and then report back to [name].

Outcome Measurements:

The primary outcomes will be a timed walking speed over 10 meters by the blinded physical therapist and the ARAT for UE function performed by the blinded therapist. These will be obtained at baseline, then after 4 weeks on assigned medication, within 5 days of the last medication dose (8 weeks) and again at 6 months post stroke onset.

Secondary outcomes obtained at the end of drug treatment and at 6 months after stroke onset by the blinded observer will include the Fugl-Meyer Motor Assessment score for both lower and upper extremities, clinic-based 3-min walking distance, and the Stroke Impact Scale score related to quality of life. We will also assess for satisfaction and self-efficacy for practice and exercise (see Table). Exploratory studies will examine dose of practice based on LEAP data (duration, number of repetitions of reach and grasp of objects) and for walking (total daily walking practice time, sedentary time, and walking bouts of more than 5 minutes), and self-ratings about self-efficacy for exercise.

Statistical Analyses:

A recent observational trial (Lohse and Lang, 2016) found that walking speed increases at 0.1m/s per month and the ARAT increases by 2.9 points monthly within the time frame as this trial.

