For the walking speed outcome, the evaluable sample size of 30 in each group will have 80% power to detect a difference in means of -0.206 (m/s), the difference between an assumed usual care walking speed of 0.51 (SD=0.28) and an assumed intervention group mean walking speed of 0.716. This assumes that the common standard deviation in the two groups and a two group t-test with a 0.05 two-sided significance level. The estimates for the mean and standard deviation for walking speed come from the LEAPS RCT (Duncan, N Engl J Med, 2011). We plan to enroll 66 patients to account for an expected 10% drop-out rate. The t-test used for the power calculation is a simplification of the mixed effects analysis plan for the primary endpoints.

For the ARAT sum score, analysis is based on a statistical power of 80% with an alpha of 5% for detecting a meaningful difference of 6 points, i.e., a 10% change, which has been suggested by several completed trials. In a stroke trial, the standard deviation was 8 points measured at 2 weeks post stroke. Again, a sample size of 60 plus 10% dropout rate should suffice.

Primary Analyses: As appropriate, t-tests, Wilcoxon rank sum, or chi-square tests will be employed to evaluate differences in baseline clinical characteristics between trial participants. Using the mixed effects model for *Hypothesis 1* should provide greater power than the t-test as it will account for the repeated observations of the endpoints over time. For *Hypothesis 2*, we will look at one aspect of the feasibility of home-based practice as the ratio of those who achieve at least 150 minutes of weekly walking (composed of bouts that exceed 5 minutes) and 100 minutes of weekly upper extremity practice using the LEAP with the whole group as the denominator. We anticipate that >75% will achieve this by the end of the intervention, based upon our preliminary studies using these devices in a chronic hemiparetic stroke population.

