Secondary Analyses: Secondary outcomes listed in the Table will be evaluated using t-tests, Wilcoxon rank sum tests, or chi-square tests as appropriate. One planned secondary analysis will compare outcomes based on whether or not participants can extend their wrist and at least 3 fingers at least 5 degrees at time of randomization, to assess for possible differences in drug responses between those with higher compared to lower levels of initial motor control. Another will compare outcomes in those who achieve the practice goals of Hypothesis 2 to those who do not in relation to drug assignment. We will not likely have enough subjects to do more than look for interesting potential future hypotheses.

Safety Committee:

A Safety Committee will serve both research sites. It will include the study statistician, a physician and an allied health clinician with training in stroke rehabilitation. It will meet before the start of the trial, every 6 months, after the first 10 subjects have completed the 2-month drug intervention, and as needed (e.g., serious adverse reaction).

Confidentiality:

All data will be entered from the study sites at UCLA, Yale and Burke into the RedCap database that will be monitored at UCLA by the study statistician for completeness. All materials related to the trial for UCLA entries will be stored in a locked cabinet in a locked room by the coordinator.

References

Dobkin BH. A Rehabilitation-Internet-of-Things in the Home to Augment Motor Skills and Exercise Training. *Neurorehabil Neural Repair*. 2016 Nov 23. pii: 1545968316680490.

Table. Measurement tools and testing schedule

Category	Test	Schedule		During treatment: at end of 4 and 8 weeks	6 mo outcomes
		Entry	Weekly f/u for 2 mo		
Study Procedures					
Screening	X	X			
Inclusion/Exclusion	X	X			
Informed Consent	X	X			
AE Assessment	X		X		
Demographics	NIH standard	X			
Disability	FIM	X			X
Mobility	10-m walk speed	X		X	X
Upper extremity fx	ARAT	X		X	X
Overall Impairment	NIHSS	X			X
Motor Impairment	Fugl-Meyer motor score	X		End of tx	X

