Exercise capacity	6-min walk distance; change in heart rate	X		X	X
Lesion location and subtype	UCLA stroke anatomy form	X			
Walking activity sensors	Duration, distance, speed for bouts; sedentary time	X	X		
Upper extremity practice from sensors	Repetitions, sets	X	X		
Self-reported activity levels pre-stroke	IPAQ	X			
Self-reported activity levels post-entry	IPAQ			X	X
Depression	CES-D	X		End of tx	X
HRQOL	Stroke Impact Scale v3.0	X		End of tx	X
Sensor usage survey	Likert scale			End of tx	
Cognition	MOCA	X			X
Exercise expectations	MOEES	X			X
Social support for activity	Likert scale	X		End of tx	X
Exercise enjoyment	PACES	X		End of tx	X
Self-efficacy for activity	ESFS	X		End of tx	X

To include record of reasons for non-participation.

Adverse events=AE; Center for Epidemiological Studies Depression Scale = CES-D;

Exercise Self-Efficacy Scale=ESFS; Functional Independence Measure=FIM;

International Physical Activity Questionnaire short form=IPAQ; metabolic equivalent minutes per week=METm/wk; Multidimensional outcome expectations for exercise scale=MOEES; Physical Activity Enjoyment Scale=PACES

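### A secondary outcome is named as a 3-minute walking distance, but the baseline list and the Table that defines the secondary analyses contain only a 6-minute walk (minor)

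*Combined protocol and SAP*

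**What the plan says.** Four places in the protocol bear on this outcome.

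- **Outcome Measurements** introduces the "Secondary outcomes obtained at the end of drug treatment and at 6 months after stroke onset by the blinded observer" and includes among them "clinic-based 3-min walking distance, and the Stroke Impact Scale score related to quality of life".
- **Baseline Studies** lists the entry assessments. The walking measures there are the 10-m "walking speed, 6-min walking distance, a video-recorded assessment of upper extremity kinematics". The only timed distance is the 6-minute one.
- **Table, Measurement tools and testing schedule**, has an exercise-capacity row reading "6-min walk distance; change in heart rate". It is marked at entry, during treatment and at 6 months. The Table has no row for a 3-minute walk.
- **Secondary Analyses** states: "Secondary outcomes listed in the Table will be evaluated using t-tests, Wilcoxon rank sum tests, or chi-square tests as appropriate".

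The 3-minute walk is mentioned once in the document and the 6-minute walk twice. No section says that one replaces or supplements the other.

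**The concern.** The duration of a timed walk is part of the outcome's definition. Here the definition depends on which section is read. Outcome Measurements gives one test, and the section that assigns the analysis points to a Table that holds a different one.

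The stake is limited but real. A reader cannot tell from the plan which distance will be reported as the secondary outcome. If a 3-minute walk were done at follow-up, it would fall outside the set of outcomes that Secondary Analyses covers, and there would be no entry value from the same test. If the 6-minute walk is done as scheduled, the text naming the outcome is wrong. The question should be settled before unblinded analysis, so that the choice of test cannot appear to depend on the results.

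**Working it through.** **Part 1: comparing the sections.** No arithmetic applies to the mismatch itself.

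| Question | 3-minute walk | 6-minute walk |
|---|---|---|
| Named as a secondary outcome in Outcome Measurements? | Yes | No |
| Entry value in Baseline Studies? | No | Yes |
| Row and visits in the Table? | No | Yes: entry, during treatment, 6 months |
| Covered by Secondary Analyses through the Table? | No | Yes |

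Two other entries might seem to fill the gap, but neither does. The 10-m walk measures speed and is a primary outcome. The walking-sensor row in the Table records home activity, whereas Outcome Measurements specifies a clinic-based test. The contradiction therefore stands, and the 6-minute walk is the only test with both an entry value and a Table row.

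**Part 2: the separate improvement.** Because an entry 6-minute distance is already collected, the follow-up comparison can be adjusted for it.

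The documents give no planning values for distance, so the only stated figure available for reproduction is the one for walking speed. Statistical Analyses uses "an assumed usual care walking speed of 0.51 (SD=0.28) and an assumed intervention group mean walking speed of 0.716", with 30 evaluable per arm and a two-sided 5% t-test.

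- Difference: 0.716 − 0.51 = 0.206 m/s.
- Standardised difference: 0.206 / 0.28 = 0.736.
- Power with 58 df: 80.0%, which matches the plan's 80%.

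If r is the correlation between entry and follow-up distance, then:

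- residual SD under ANCOVA = SD × sqrt(1 − r²)
- detectable difference at fixed power ≈ unadjusted detectable difference × sqrt(1 − r²)

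| Assumed r | sqrt(1 − r²) | Reduction in detectable difference |
|---|---|---|
| 0.3 | sqrt(0.91) = 0.954 | about 5% |
| 0.5 | sqrt(0.75) = 0.866 | about 13% |
| 0.7 | sqrt(0.51) = 0.714 | about 29% |

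These percentages need only r. To put them in metres, one has to borrow the walking-speed values and assume a constant pace for 360 s:

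- SD: 0.28 × 360 = 100.8 m
- Difference: 0.206 × 360 = 74.2 m

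With 57 df, the difference detectable with 80% power then falls from about 74 m unadjusted to 70.8, 64.2 and 53.0 m at r = 0.3, 0.5 and 0.7. Power for 74.2 m rises from 80.0% to 83.6%, 89.9% and 97.5%. The metre figures are illustrative only, since the plan states no SD or target difference for distance.

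**The case against.** The strongest reply is that this is an obvious slip. Two mentions of 6 minutes stand against one of 3, and staff working from the Table would do the 6-minute walk at every visit. That argument stands as far as it bears on severity. It does not remove the contradiction, because the documents alone cannot confirm intent. The list in Outcome Measurements is open-ended, and nothing expressly excludes a separate 3-minute measure. The Table is a schedule that mixes screening items, primary outcomes and sensor data, and it labels no row as secondary. It makes the 6-minute reading more likely without proving it. For that reason the sites' practice should be confirmed before the text is corrected.

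A second reply is that the ANCOVA suggestion is a preference. This also stands in part. An unadjusted comparison in a randomised trial is valid, ANCOVA does not cure the wording conflict, and the gain depends on an assumed r. It is therefore kept separate. The plan itself argues, for its primary outcomes, that a mixed model using the repeated observations should have more power than a t-test.

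Three stronger readings are tempting, and the documents do not support them:

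- **That a spurious fall in distance will be reported.** At 0.51 m/s and constant pace, 6 minutes gives 183.6 m and 3 minutes gives 91.8 m, so subtracting one from the other would show about −92 m in someone unchanged. The plan nowhere calls for that subtraction, and Secondary Analyses does not specify change scores. The arms could still be compared at follow-up on either test.
- **That sites may be using different tests unnoticed.** Nothing shows a difference between sites. "A data manager at UCLA will review all incoming data from the 3 sites for completeness and quality", and data go into a "RedCap database that will be monitored at UCLA by the study statistician for completeness". Both arrangements make unnoticed mixing less likely.
- **That the Table's visits contradict the text.** The Table marks the 6-minute walk at weeks 4 and 8, while Outcome Measurements names end of treatment and 6 months. A week-4 walk can be measured without being an outcome time point, so this is not a contradiction.

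**Conclusion.** The inconsistency is real and in the current text. As written, the 3-minute walking distance has no scheduled assessment, no same-test baseline and no assigned analysis. The severity is minor: one secondary outcome is ambiguously defined, the likely cause is editorial, and following the Table leaves nothing to repair except the text. Confidence in the mismatch is high, and it rests on no numerical assumption.

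Using one test throughout loses no power, so the reductions of about 5%, 13% and 29% do not measure harm from the mismatch. They measure what baseline adjustment could add, given the assumed values of r.

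**What to change.** 1. **Reconcile the sections to one test.** Confirm with the three sites which walk they perform. If it is the 6-minute walk, correct the duration in Outcome Measurements so that it agrees with Baseline Studies and the Table.
2. **Keep the two durations apart.** If any 3-minute distances have been collected, do not pool them with 6-minute distances.
3. **Separate and optional.** Add a sentence to Secondary Analyses stating that 6-minute distances at end of treatment and at 6 months are compared between arms by ANCOVA adjusted for the entry 6-minute distance, instead of by an unadjusted t-test.

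The cost is a query and note to three sites, a one-word correction, and one sentence if the third item is adopted. No new assessment is needed, because the 6-minute walk is already scheduled at entry, during treatment and at 6 months.
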